### **5.8 Subject Withdrawal/Discontinuation Criteria**

Subjects may withdraw consent at any time for any reason or be dropped from the trial at the discretion of the investigator should any untoward effect occur. In addition, a subject may be withdrawn by the investigator or the Sponsor if enrollment into the trial is inappropriate, the trial plan is violated, or for administrative and/or other safety reasons. Specific details regarding discontinuation or withdrawal procedures; including specific details regarding withdrawal from Future Biomedical Research, are provided in Section 7.1.4 – Other Procedures.

In this trial, a subject may discontinue from treatment but continue to participate in the regularly scheduled activities, as long as the subject does not withdraw consent. Once a subject has discontinued treatment, even though he/she continues to be monitored in the trial, he/she may be allowed to begin treatment again if deemed medically appropriate.

A subject must be discontinued from the trial for any of the following reasons:

- The subject or legal representative (such as a parent or legal guardian) withdraws consent.

A subject must be discontinued from treatment (but may continue to be monitored in the trial) for any of the following reasons:

- The subject or legal representative (such as a parent or legal guardian) withdraws consent for treatment
- Confirmed radiographic disease progression

*Note:* For unconfirmed radiographic disease progression, please see Section 5.2.2.

*Note:* A subject may be granted an exception to continue on treatment with confirmed radiographic progression if clinically stable or clinically improved, please see Section 7.1.2.6.3.

- Unacceptable adverse experiences as described in Section 5.2.1.2
- Intercurrent illness that prevents further administration of treatment
- Investigator's decision to withdraw the subject
- The subject has a confirmed positive serum pregnancy test

- Noncompliance with trial treatment or procedure requirements
- The subject is lost to follow-up
- Completed 24 months of treatment with pembrolizumab (MK-3475)

*Note: 24 months of study medication is calculated from the date of first dose. Subjects who stop pembrolizumab (MK-3475) after 24 months may be eligible for up to one year of additional study treatment if they progress after stopping study treatment provided they meet the requirements detailed in Section 7.1.5.2.1.*

- Administrative reasons

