prior to the first dose of trial treatment for required lab tests). Screening number will be assigned when the study informed consent is signed. 
 
f. Signing the informed consent for future biomedical research (FBR) sample is optional. Detailed instructions for the collection and management of specimens for FBR are provided in the appendices of the Central Lab Manual and Section 12.2 of the Protocol.
 
g. Prior medications – Record all medications taken within 30 days of the screening visit. Concomitant medications – Enter new medications started during the trial through the Safety Follow-up visit. Record all medications taken for SAEs as defined in Section 7.2.
 
h. Trial treatment may be administered up to 3 days before or after the scheduled Day 1 of each cycle due to administrative reasons. Sites should make every effort to target infusion timing to be as close to 30 minutes as possible. However, given the variability of infusion pumps from site to site, a window of -5 minutes and +10 minutes is permitted (i.e., infusion time is 30 minutes: -5 min/+10 min). The reason for any delay in infusion outside of the protocol specified window should be documented in the patient's chart and recorded on the eCRFs.
 
i. Record all AEs occurring within 30 days after the last dose of trial treatment. Report all SAEs (related and unrelated to trial treatment) and ECIs occurring up until 90 days after the last dose of trial treatment or the start of new anti-cancer treatment, whichever comes first. Afterwards, report only SAEs and ECIs that are related to trial treatment.
 
j. To be repeated every 2 cycles after Cycle 6 up to 1 year.
 
k. Vital signs to include temperature, pulse, respiratory rate, weight and blood pressure. Height will be measured at visit 1 only.
 
l. For women of reproductive potential, a serum pregnancy test should be performed within 72 hours prior to first dose of trial treatment. A urine test can be considered if serum is not appropriate. Pregnancy tests (serum and/or urine tests) should be repeated if required by local guidelines.
 
m. Coagulation factors (PT/INR and aPTT) should be tested as part of the screening procedures for all subjects. Any subject receiving anticoagulant therapy should have coagulation factors monitored closely throughout the trial.
 
n. Laboratory tests for screening are to be performed within 10 days prior to the first dose of trial treatment. See Section 7.1.3 for details regarding laboratory tests.
 
o. After Cycle 1, lab samples can be collected up to 72 hours prior to the scheduled time point. See Section 7.1.3 for details regarding laboratory tests.
 
p. Unresolved abnormal labs that are drug related AEs should be followed until resolution. Labs do not need to be repeated after the end of treatment if labs are within normal range.
 
q. Pre-dose trough PK and anti-pembrolizumab (MK-3475) antibody samples will be collected at Cycles 1, 2, 4, 8, and every 4 cycles thereafter. All pre-dose trough samples should be drawn within 24 hours before infusion of pembrolizumab (MK-3475). Additional post-dose peak PK samples will be drawn within 30 minutes after end of pembrolizumab (MK-3475) infusion at Cycles 1 and 8. An additional, single PK sample should be drawn between 72 and 168 hours after Cycle 1 dosing.
 
r. Blood for correlative studies should be collected prior to Cycle 1, Cycle 2, Cycle 3 and again at treatment discontinuation.
 
s. The initial tumor imaging will be performed within 28 days prior to the first dose of trial treatment and must be sent to the central vendor to confirm measurable disease for study eligibility. Imaging should include the head, neck, chest, and abdomen; imaging of the pelvis is optional (refer to Section 7.1.2.6). Scans performed as part of routine clinical management are acceptable for use as the screening scan if they are of diagnostic quality, meet the requirements specified by the protocol, and are performed within 28 days prior to the first dose of trial treatment.
 
t. The first on-study imaging time point will be performed at 9 weeks (± 7 days) after first dose of study treatment and then every 6 weeks (± 7 days) thereafter or more frequently if clinically indicated. After 1 year, imaging time point will occur every 9 weeks (± 7 days). Imaging timing should follow calendar days and should not be adjusted for delays in cycle starts or extension of pembrolizumab (MK-3475) cycle frequencies. Imaging should include the head, neck, chest, and abdomen; imaging of the pelvis is optional (refer to Section 7.1.2.6). The same imaging technique should be used in a subject throughout the trial. On-study scans, including the baseline scans, should be submitted immediately to the central imaging vendor.
 
u. Baseline tumor tissue for biomarker analysis from a newly obtained core or excisional biopsy (FNA not adequate) must be provided to the central vendor for PD-L1 biomarker testing. Confirmation of tissue adequacy should be received from the central vendor prior to the first dose of trial treatment. A “newly obtained” sample may be obtained up to 42 days prior to
 
											

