#### **7.1.2.6.2 Tumor Imaging During Trial**

The first imaging assessment should be performed at 9 weeks (63 days  $\pm$  7 days) from the date of 1st dose. Subsequent imaging should be performed every 6 weeks (42 days  $\pm$  7 days), more frequently if clinically indicated. Subjects who remain on treatment for a year will have imaging performed every 9 weeks. Imaging should not be delayed for delays in cycle starts.

Per RECIST 1.1, response should be confirmed by a repeat radiographic assessment not less than 4 weeks from the date the response was first documented. The scan for confirmation of response may be performed at the earliest 4 weeks after the first indication of response, or at the next scheduled scan (6 weeks later), whichever is clinically indicated. Imaging should then return to the original schedule beginning with the next protocol-specified timepoint. Subjects who obtain a confirmation scan at 4 weeks do not need to undergo the next scheduled imaging assessment if it is due < 4 weeks later; imaging may resume at the subsequent scheduled timepoint. (e.g. If a subject obtains a scan at Week 13 to confirm a Week 9 response, they will not be required to complete the scheduled Week 15 scan. The next imaging would then occur at Week 21 as usual.)

Imaging should continue to be performed until radiographic disease progression, the start of new anti-cancer treatment, withdrawal of consent, death, or notification by the Sponsor, whichever occurs first. Disease progression may be confirmed at least 4 weeks after the first scan indicating progressive disease in clinically stable subjects. Subjects who have unconfirmed disease progression may continue on treatment until progression is confirmed provided they have met the conditions detailed in Section 7.1.2.6.3.

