### 8.2.3.1 Efficacy/Immunogenicity/Pharmacokinetics Endpoints

The primary efficacy endpoint is objective response rate (ORR), defined as the proportion of subjects in the analysis population who have complete response (CR) or partial response (PR) using RECIST 1.1 criteria at any time during the study. Response for the primary analyses will be determined by independent radiology review. ORR will be evaluated separately in all subjects and the subset of all PD-L1 strong positive subjects (defined as a PD-L1 tumor proportion score  $\geq 50\%$  by IHC).

Supportive analyses of ORR will be performed based on site assessments using RECIST 1.1.

ORR in all subjects with any PD-L1 positive will be a key secondary efficacy endpoint. PD-L1 positivity is defined as PD-L1 tumor proportion score  $>0\%$  by IHC. Other key secondary efficacy endpoints that will be evaluated in all subjects, all PD-L1 positive subjects, and all PD-L1 strong positive subjects include:

**Duration of Response:** defined as time from first RECIST 1.1 response to disease progression in subjects who achieve a PR or better

**ORR by modified RECIST 1.1:** defined as proportion of subjects with a CR or PR using modified RECIST 1.1 criteria as defined in Section 4.2.3.1.

**ORR among HPV positive subjects:** defined as the proportion of subjects with HPV positive tumor biopsy who achieve a CR or PR according to RECIST 1.1 criteria.

**Progression-free survival (PFS):** defined as the time from allocation to the first documented disease progression according to RECIST 1.1 or death due to any cause, whichever occurs first.

**Overall survival (OS):** defined as the time from allocation to death due to any cause.

Additional exploratory endpoints include PFS by modified RECIST 1.1 criteria and ORR/PFS/OS by exploratory candidate biomarkers.

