## **8.2.4 Analysis Populations**

### **8.2.4.1 Efficacy Analysis Populations**

The Full Analysis Set (FAS) population will serve as the primary population for the analysis of efficacy data in this study. The FAS population consists of all subjects who:

- Receive at least one dose of study treatment,
- Have a baseline scan with measurable disease per RECIST 1.1 by independent radiology review

A supportive analysis using the All Patients as Treated (APaT) population, defined as all enrolled subjects who receive at least one dose of study medication, will be performed for the primary efficacy endpoint(s). Supportive analyses in the FAS population using the site radiology assessment will require baseline scan with measurable disease per RECIST 1.1 using site radiology assessment.

Details on the approach to handling missing data are provided in Section 8.2.5 Statistical Methods.

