Response Duration • RECIST 1.1, independent radiology review • modified RECIST 1.1, investigator	Summary statistics using Kaplan-Meier method	FAS in all below populations: 

• all-comers

• PD-L1 strong positive*

• PD-L1 positive‡

 APaT in all below populations: 

• all-comers

• PD-L1 strong positive

• PD-L1 positive

	Non-responders are excluded in analysis

Endpoint	Statistical Method	Analysis Population	Missing data approach
PFS 
 
RECIST 1.1, independent radiology review
 
modified RECIST 1.1, investigator
 
	Summary statistics using Kaplan-Meier method	FAS in all below populations: 
 
all-comers
 
PD-L1 strong positive*
 
PD-L1 positive‡
 
 APaT in all below populations: 
 
all-comers
 
PD-L1 strong positive
 
PD-L1 positive
 
	Censored at last assessment date
OS 
 
RECIST 1.1, independent radiology review
 
modified RECIST 1.1, investigator
 
	Summary statistics using Kaplan-Meier method	FAS in all below populations: 
 
all-comers
 
PD-L1 strong positive*
 
PD-L1 positive‡
 
 APaT in all below populations: 
 
all-comers
 
PD-L1 strong positive
 
PD-L1 positive
 
	Censored at last assessment date

\* PD-L1 strong positive is defined as PD-L1 tumor proportion score  $\geq 50\%$  by IHC.  
 ‡ PD-L1 positive is defined as PD-L1 tumor proportion score exceeding 0% by IHC.  
 ¶ Exact Clopper-Pearson 95% CI will be provided.

Exploratory analyses of PFS using modified RECIST 1.1 criteria and PFS/OS by exploratory candidate biomarkers will also follow the same approach as for the secondary analyses of PFS and OS. The exploratory analysis of ORR by PD-L1 combined positive score (CPS) and exploratory candidate biomarkers will be conducted using point estimate and exact binomial CI.

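### PFS and OS start at allocation but only dosed subjects are analysed, so any wait for the first dose adds time in which no death can be counted; small, and confined to two secondary endpoints

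*Combined protocol and SAP*

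**What the plan says.** - **Time origin (8.2.3.1).** PFS is "defined as the time from allocation to the first documented disease progression according to RECIST 1.1 or death due to any cause". OS is "defined as the time from allocation to death due to any cause".
- **Analysis sets (8.2.4.1).** The first FAS condition is "Receive at least one dose of study treatment"; the second is measurable disease at baseline by independent review. APaT is "defined as all enrolled subjects who receive at least one dose of study medication".
- **Where they meet (8.2.5.1, Table 10).** The PFS and OS rows list FAS and then "APaT in all below populations". The method is Kaplan-Meier, and neither endpoint is tested.
- **Scan clock.** Section 7.1.2.6.2 sets the first on-study scan at 63 days ± 7 "from the date of 1 st dose". Footnote t of 6.1.1 agrees: "The first on-study imaging time point will be performed at 9 weeks (± 7 days) after first dose of study treatment".
- **Time from allocation to dosing.** Section 5.2 asks for dosing on the allocation date or as near to it as can be managed. The 6.1.1 flow chart shows +3 days for Cycle 1. Footnote d, attached to that entry, sets a limit of 3-5 days counted from enrollment.
- **Subjects with no data (8.2.5.1).** They are censored at Day 1, which that section does not define. In 5.2 and 5.2.2, Day 1 is the dosing day of a cycle.

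No section equates allocation with first dose, and none gives a first-dose version of PFS or OS.

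**The concern.** Entry to both analysis sets depends on something that happens after the clock starts. A subject who is allocated and dies before dosing is in neither FAS nor APaT. Everyone analysed has therefore survived the interval, and the interval still counts as survival time. The safety sections do recognise it: under 7.2.3.1, reporting of serious events and of deaths other than from progression starts at allocation. Such a death would be reported but could never enter OS.

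For PFS the same holds for the death component. Progression is nearly as constrained, because every scheduled on-study scan is timed from first dose.

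At stake are the Kaplan-Meier curves and medians for two endpoints that 8.2.3.1 lists as key secondary. The shift goes in the favourable direction, and a single-arm trial has no concurrent arm carrying the same shift.

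**Working it through.** **1. The plan's own figure.** The documents give no event count, assumed median or power for PFS or OS. The only sizing figure is for ORR (8.2.7): 14 responses in 135 to reject 5% at one-sided 1.25%. It reproduces with the exact binomial: P(X ≥ 14) = 0.0079, below 0.0125; P(X ≥ 13) = 0.0181, above it. The test counts responders, so no time origin enters.

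**2. Mechanism.** For a dosed subject with an event after dosing,

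time from allocation = G + time from first dose,

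where G ≥ 0 is the gap. If G is the same for everyone, the Kaplan-Meier curve and its median move right by exactly G.

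**3. Size of G.** With same-day dosing, G = 0. If the Cycle 1 windows count from allocation (an assumption), G is at most 3 days by the flow chart, or 5 days by the upper end of footnote d. With 30.44 days to a month:

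- 3 / 30.44 = 0.099 month
- 5 / 30.44 = 0.164 month

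If gaps were spread evenly over 0-3 days (an assumption; no distribution is given), simulation moves the OS median by about 1.5 days, or 0.05 month.

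**4. Scale for OS.** The 6.7-month methotrexate median in 4.1.2 serves only as a yardstick. 6.7 × 30.44 = 203.9 days, so 3 / 203.9 = 1.5% and 5 / 203.9 = 2.5%.

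For sampling error, take n = 135, exponential survival and no censoring:

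- SE of the median = 6.7 / (ln 2 × √135) = 6.7 / 8.05 = 0.83 month (simulation also gives 0.83)
- 95% half-width = 1.96 × 0.83 = 1.63 months
- 0.099 / 1.63 = 6%; 0.164 / 1.63 = 10%

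Under the same model, 6-month survival rises by 0.55 percentage points (3 days) or 0.92 (5 days).

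**5. Scale for PFS.** If the median fell at the first scan (63 days, an assumption), 3 / 63 = 4.8% and 5 / 63 = 7.9%. Over the permitted 56-70 days the ranges are 4.3-5.4% and 7.1-8.9%. The ±7-day window on that scan is wider than either gap.

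**6. Deaths that cannot be counted.** At a constant hazard with a 203.9-day median, 150 × (1 − exp(−ln 2 × 3 / 203.9)) = 1.5 deaths in 3 days, and 2.5 in 5 days. This also shows scale only.

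**The case against.** The strongest reply is that the effect is immaterial. PFS and OS are descriptive, the sampling error is far larger than the shift, and permitted scan timing can move a PFS date by more than the choice of origin can. Section 5.2 also pushes the gap towards zero. All of this stands, and it sets the severity. It does not show that the definition fits the analysis sets.

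Two stronger readings are tempting and go beyond the text:

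- **That the gap is free of any PFS event by construction.** This is strict for death only. Section 7.1.2.6.2 allows extra scans when clinically warranted, and 7.1.2.6 sends unscheduled images to the central vendor. Progression seen in the gap in a subject who is then dosed would be unusual but is not excluded.
- **That the gap is known to be at most 3 days, or 5.** The +3 entry carries footnote d, and footnote d counts from enrollment. The documents do not say that enrollment means allocation, so both limits depend on the same unstated link.

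A reader might also point to clocks that already start at first dose, such as 5.8 ("24 months of study medication is calculated from the date of first dose") and Days on Therapy in 8.2.10. Those measure drug exposure and have to start there. They show that the date is available, not that survival endpoints must use it.

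Finally, moving the origin does not bring back pre-dose deaths. That is true. Keeping allocation and analysing all allocated subjects would also be coherent and would count them, but it needs an analysis set that the plan does not have.

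**Conclusion.** The mismatch is real: the clock starts at allocation, while the analysis sets are fixed by dosing. Any gap lengthens OS, and almost always PFS. The shift is zero with same-day dosing. It is up to 0.10 or 0.16 month if the 3-day or 5-day window counts from allocation, which the documents leave open. The comparison with sampling error (about 6-10% of the OS half-width) rests on a 6.7-month median, 135 subjects, exponential survival and no censoring.

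A reader might infer that the efficacy conclusions are biased. The documents do not support that: ORR and its tests have no time origin, response duration starts at first response, and no hypothesis depends on PFS or OS. This is a cheap improvement to two definitions, nice to have rather than necessary.

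**What to change.** - In 8.2.3.1, define PFS and OS as running from the date of first dose of study treatment.
- In 8.2.5.1, state that Day 1 in the censoring rule is that same date. This is for consistency and has almost no numerical effect.

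The cost is one phrase in each of two definitions and one clarification. No new data are needed, because the first-dose date already anchors imaging and the 24-month limit. Section 8.0 says there will be no separate SAP, so the edit belongs in the protocol text. The change of origin must be documented in an amendment with its reason, because the trial is open-label and already running. The reason is easy to give, since the change can only shorten the estimates. The downside is that PFS and OS become shorter by whatever the gap was.

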### 8.2.3.2 Safety Endpoints

A description of safety measures is provided in Section 4.2.3.2.

The primary safety endpoints are AEs graded using CTCAE (Version 4.0) criteria. Safety will be assessed by quantifying the toxicities and grades experienced by subjects who have received pembrolizumab (MK-3475), including serious adverse events (SAEs) and events of

clinical interest (ECIs). Immune-related ECIs, as described in Section 7.2.3.2 will be collected. Other safety endpoints include laboratory safety assessments, ECOG performance status, vital signs and physical examinations.

## **8.2.4 Analysis Populations**

### **8.2.4.1 Efficacy Analysis Populations**

The Full Analysis Set (FAS) population will serve as the primary population for the analysis of efficacy data in this study. The FAS population consists of all subjects who:

- Receive at least one dose of study treatment,
- Have a baseline scan with measurable disease per RECIST 1.1 by independent radiology review

A supportive analysis using the All Patients as Treated (APaT) population, defined as all enrolled subjects who receive at least one dose of study medication, will be performed for the primary efficacy endpoint(s). Supportive analyses in the FAS population using the site radiology assessment will require baseline scan with measurable disease per RECIST 1.1 using site radiology assessment.

Details on the approach to handling missing data are provided in Section 8.2.5 Statistical Methods.

### **8.2.4.2 Safety Analysis Populations**

The All Patients as Treated (APaT) population will be used for the analysis of safety data in this study.

At least one laboratory or vital sign measurement obtained subsequent to at least one dose of study treatment is required for inclusion in the analysis of each specific parameter. To assess change from baseline, a baseline measurement is also required.

Details on the approach to handling missing data for safety analyses are provided in Section 8.2.5 Statistical Methods.

## **8.2.5 Statistical Methods**

Statistical testing and inference for safety analyses are described in 8.2.5.2. Efficacy results that will be considered to be statistically significant after consideration of the strategy for controlling the Type I error are described in Section 8.2.6, Multiplicity. Nominal p-values may be computed for other efficacy analyses as a measure of strength of association between the endpoint and the treatment effect rather than formal tests of hypotheses.

